5.1 Research treatment

5.1.1 Treatment protocol

Each subject received a treatment regimen of 1 bag of amino acid peritoneal dialysis and 2-4 bags of glucose peritoneal dialysis fluid daily for 6 months (the amount of glucose peritoneal dialysis fluid was determined based on the treatment plan at the time of

screening when the patient entered the study). The amino acid peritoneal dialysis fluid was provided by the research center, with the following composition: amino acids (15). The peritoneal dialysis fluid was also supplied by the research center, containing the following components in each 1L solution: 1000 mL, alanine 0.951g, arginine 1.071g, glycine 0.510g, histidine 0.714g, isoleucine 0.850g, leucine 1.020g, lysine hydrochloride 0.955g, methionine 0.850g, phenylalanine 0.570g, proline 0.595g, serine 0.510g, threonine 0.646g, tryptophan 0.270g, tyrosine 0.300g, arginine 1.393g, sodium chloride 5.380g, calcium chloride ($\text{CaCl}_2 \cdot 2\text{H}_2\text{O}$) 0.184g, magnesium chloride ($\text{MgCl}_2 \cdot 6\text{H}_2\text{O}$) 0.051g), and sodium lactate 4.480g, equivalent ion concentration (mmol/L): amino acid 87.16mmol/L, sodium 132mmol/L, calcium 1.25mmol/L,

Magnesium 0.25mmol/L, chlorine 105mmol/L, lactate 40mmol/L, the excipients of this product are hydrochloric acid and water for injection. This product is a peritoneal dialysis solution without grape, which is used as part of the peritoneal dialysis program for the treatment of chronic kidney patients

It is not suitable for peritoneal dialysis patients with serum albumin less than 35g/L.

The components of the glucose peritoneal dialysate are shown in Figure 2. The use of one bag of amino acid peritoneal dialysate is scheduled during nighttime sleep, while the use of 2-4 bags of glucose peritoneal dialysate is scheduled during daytime hours. The total daily infusion volume, each infusion volume, each dwell time, and each effluent volume for each participant are determined by the researchers based on the patient's condition

Individual circumstances and standardized prescriptions are adjusted.

5.1.2 Treatment dose adjustment

During the treatment, according to the changes of the patient's ultrafiltration volume, blood pressure, biochemical blood, nutritional status and other indicators, the researchers can adjust the dosage and frequency of treatment appropriately to ensure the patient's water and electrolyte balance and metabolic stability. Specifically, the adjustment principles are as follows:

If the patient develops signs of water retention such as weight gain, edema, and hypertension, the researcher can increase the frequency of amino acid peritoneal dialysis or increase the concentration of glucose peritoneal dialysis to increase ultrafiltration and reduce water Sub-daily intake.

If the patient shows signs of water loss such as weight loss, hypotension, and hypoglycemia, the researcher can reduce the number of times of amino acid peritoneal dialysis fluid or reduce the concentration of glucose peritoneal dialysis fluid to reduce the amount of ultrafiltration and increase water intake.

If the patient shows signs of elevated or decreased blood potassium, the investigator can administer drug therapy to replenish potassium, to maintain normal blood potassium levels. If the patient shows signs of elevated or decreased blood calcium, the investigator can adjust the patient's calcium and vitamin D. The dosage of the drug is to maintain the blood calcium level within the normal range.

If the patient shows a decrease in nutritional indicators such as serum albumin, prealbumin, nPCR, and nPNA, the researcher can increase the number of times or volume of amino acid peritoneal dialysis to provide more amino acids and energy, and give patients appropriate nutritional support and education.

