Peritoneal dialysis is a treatment method that uses the peritoneum as a semipermeable membrane. By injecting dialysate into the abdominal cavity, metabolic waste and excess water in the blood are allowed to permeate and diffuse into the dialysate, which is then drained from the body. This process helps remove toxins from the body and regulate electrolyte balance. Peritoneal dialysis has several advantages, including ease of operation, no need for an intravenous access, minimal impact on hemodynamics, the ability to preserve residual kidney function, and the flexibility to control treatment time and location. It is widely used as a substitute for kidney therapy in patients with end-stage chronic renal failure method.

However, long-term peritoneal dialysis can also lead to some adverse consequences, one of which is malnutrition. Malnutrition refers to a state where the nutrients ingested or absorbed by the body cannot meet its physiological needs, leading to dysregulation in the body's composition, function, or metabolism. Malnutrition is very common among patients undergoing maintenance peritoneal dialysis, with an incidence rate as high as 20% to 70%. The causes of malnutrition are numerous, including metabolic disorders due to reduced kidney function, decreased appetite, gastrointestinal symptoms, restricted diets, and medication use. Additionally, peritoneal dialysis itself can exacerbate the development of malnutrition its development is mainly manifested in: loss of proteins and amino acids: about 5 to 15g of protein is excreted daily through peritoneal dialysis fluid, of which about half is albumin. At the same time, about 10 to 20g of free amino acids are lost daily. These proteins and the loss of amino acids leads to negative nitrogen balance and decreased serum albumin levels.

Glucose absorption: Conventional peritoneal dialysis fluids contain high concentrations of glucose as a osmotic agent to increase the amount of water filtered. However, these glucose are also absorbed by the body, about 80-120g per day. These additional energy intake can lead to metabolic disorders such as obesity, hyperinsulinemia, insulin resistance and diabetes.

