Treatment Phase: The treatment phase begins after enrollment. Each participant receives a regimen of 1 bag of amino acid peritoneal dialysis and 2-4 bags of glucose peritoneal dialysis fluid daily for 6 months (the amount of glucose peritoneal dialysis fluid is determined based on the treatment plan at the time of screening when the patient enters the study). The amino acid peritoneal dialysis fluid is provided by the research center, with the following composition: amino acids (15). The glucose peritoneal dialysis fluid is also provided by the research center, with the following composition: this product is a compound preparation, each 1L the composition of the solution is 1000mL, alanine 0.951g, arginine 1.071g, glycine 0.510g, histidine 0.714g, leucine 0.850g, lysine 1.020g, 1-lysine hydrochloride 0.955g, methionine 0.850g, phenylalanine 0.570g, proline 0.595g, serine 0.510g, threonine 0.646g, tryptophan 0.270g, tyrosine 0.300g, ammonia 1.393g, sodium chloride 5.380g, Calcium chloride ($\text{CaCl}_2 \cdot 2\text{H}_2\text{O}$) 0.184g, Magnesium chloride (Mg, CL2·6H2O]0.051g), Sodium lactate 4.480g, Ion concentration (mmol/L): Amino acids 87.16mmol/L, Sodium 132mmol/L, Calcium 1.25mmol/L, Magnesium 0.25mmol/L, Chlorine 105mmol/L, Lactate root 40mmol/L. The excipients of this product include hydrochloric acid and water for injection. This product is a glucose-free peritoneal dialysis solution, used as part of the peritoneal dialysis regimen

One part is used for the treatment of chronic kidney patients, especially suitable for peritoneal dialysis patients with serum albumin less than 35g/L.

The composition of glucose peritoneal dialysis fluid is shown in Figure 2:

Drug name	composition					ion concentration					osmotic pressure	pH	capacity
	C6H12O6·H2O	NaCl	C3H5NaO3	CaCl2·2H2O	MgCl·6H2O	Na	Ca	Mg	chloride	lactate			
Low Calcium Peritoneal Dialysis Solution(lactate-G1.5%)	1.5g	0.538 g	0.448g	0.0183g	0.0051g	132.01	1.25	0.25	95.04	39.97	344	4.5-6.5	2000
Low Calcium Peritoneal Dialysis Solution(lactate-G1.5%)	2.5g	0.538 g	0.448g	0.0183g	0.0051g	132.01	1.25	0.25	95.04	39.97	395	4.5-6.5	2000
Low Calcium Peritoneal Dialysis Solution(lactate-G4.25%)	4.25	0.538 g	0.448g	0.0183g	0.0051g	132.01	1.25	0.25	95.04	39.97	483	4.5-6.5	2000

Figure 2. Composition of glucose peritoneal dialysis fluid

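### The dose-adjustment rule lists hypoglycemia as a sign of water loss and permits a lower dialysate glucose concentration in response

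*Combined protocol and SAP*

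**What the plan says.** Section 5.1.2 lets the researcher adjust treatment, with the general aim of maintaining "water and electrolyte balance and metabolic stability". Specific principles follow.

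- **Water retention.** The triggers are "signs of water retention such as weight gain, edema, and hypertension". The dialysate responses are more amino acid exchanges or a stronger glucose solution.
- **Water loss.** The example signs are weight loss, hypotension and a third, at which point the text reads "and hypoglycemia, the researcher can reduce the number of times of amino acid peritoneal dialysis fluid or reduce the concentration of glucose peritoneal dialysis fluid". The purpose clause shows that the target is fluid: "or reduce the concentration of glucose peritoneal dialysis fluid to reduce the amount of ultrafiltration and increase water intake".
- **Biochemical and nutritional signs.** These have separate lines with separate responses. One begins "If the patient shows signs of elevated or decreased blood potassium"; others cover calcium and the nutritional indicators. Blood glucose has no such line.

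The regimen in Section 4.1 includes "2-4 bags of glucose peritoneal dialysis fluid daily for 6 months", besides one glucose-free amino acid bag, used at night. Section 1 says of the glucose in conventional fluid that "these glucose are also absorbed by the body, about 80-120g per day".

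**The concern.** Two of the three example signs of water loss, weight loss and hypotension, are the opposites of signs in the water-retention list. Hypoglycemia has no counterpart there and is not a measure of volume. Listing it attaches a fluid response to a glucose problem.

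One of the two permitted responses works against a patient with low glucose, because it lowers the glucose content of the only bags that contain any. Low glucose is a plausible event in this population: diabetes is not among the exclusions in Section 3.3.2, and the concomitant treatments in Section 5.2 include no rule for glucose-lowering drugs. Neither point shows harm. They explain why the one instruction that names hypoglycemia should not point in an unhelpful direction, particularly when five centers are to apply a uniform plan (Section 9.3).

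What is at stake is patient safety at the level of a single dosing rule. No effect on the fasting-glucose endpoint is claimed.

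**Working it through.** The plan gives no figure to reproduce here. The check has two parts.

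**Reading the text**

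1. The trigger is a group of signs introduced as examples. The text does not say whether one sign alone is enough to act.
2. The responses are joined by *or* and are optional. A lower glucose concentration is therefore one of two permitted actions and is not required.
3. The stated purpose is less ultrafiltration and more water intake. For a volume-depleted patient a weaker bag serves that purpose, so the response is sound for weight loss and hypotension.
4. For hypoglycemia the purpose does not apply. Given absorption of dialysate glucose as described in Section 1, the same action reduces a glucose source.
5. No other section mentions hypoglycemia, so nothing elsewhere overrides the entry.

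**Sizing the glucose option**

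Inputs are from Figure 2 in Section 4.1: bag volume 2000 mL; glucose monohydrate 1.5, 2.5 and 4.25 g; osmotic pressure 344, 395 and 483. The strongest is labelled "Low Calcium Peritoneal Dialysis Solution(lactate-G4.25" percent.

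Assumptions: the amounts are g per 100 mL, and the row with 2.5 g is the 2.5% bag, although its label repeats 1.5%.

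- *Unit check.* NaCl 0.538 g and sodium lactate 0.448 g per 100 mL, converted with standard molar masses, give about 132.0 mmol/L sodium. Figure 2 lists 132.01.
- *Monohydrate check*, taking osmotic pressure as mOsm/L. The listed differences are 395 − 344 = 51 and 483 − 395 = 88. The monohydrate predicts 10 g/L ÷ 198.17 g/mol = 50.5 mmol/L and 17.5 g/L ÷ 198.17 g/mol = 88.3 mmol/L. These agree.

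Monohydrate removed per bag = (difference in %) ÷ 100 × 2000 mL:

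- 2.5% to 1.5%: 1.0 ÷ 100 × 2000 = 20 g
- 4.25% to 2.5%: 1.75 ÷ 100 × 2000 = 35 g

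Glucose = monohydrate × 180.16 ÷ 198.17 (0.909), giving 18.2 g and 31.8 g per bag.

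The rule does not say how many bags are stepped down, so the daily fall in instilled glucose is shown for one to four:

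| Bags stepped down | 2.5% to 1.5% (g/day) | 4.25% to 2.5% (g/day) |
|---|---|---|
| 1 | 18.2 | 31.8 |
| 2 | 36.4 | 63.6 |
| 3 | 54.5 | 95.5 |
| 4 | 72.7 | 127.3 |

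The fall in absorbed glucose is smaller and cannot be derived from the documents. For a patient already on 1.5% in every bag, no lower strength is listed and the effect is zero.

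**The case against.** The strongest objection is that this is probably a translation error. The English text has many garbled phrases, including one in Section 5.1.2 itself, and a single out-of-place word in a list of volume signs is weak evidence of what the investigators intended. If the source text is right, only the translation needs correcting. This stands as a caution about origin, and the documents cannot settle it. But the word is a clear term in an intact sentence of an operative dosing rule, and that is the rule as it now reads.

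Second, the trigger is water loss and the aim is fluid balance; nothing offers a weaker bag as treatment for hypoglycemia. The unwanted case requires a site to read isolated low glucose as water loss and then choose the glucose option over the other. That is correct and limits the likelihood. It does not explain why the word belongs in the list.

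Third, there are safeguards. The rule is permissive, its opening sentence directs adjustment by blood biochemistry among other indicators, Section 5.2 allows other necessary drug treatment, and Section 6.2 requires appropriate care of adverse events. All of these reduce the risk; none corrects the entry.

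Fourth, Section 1 presents glucose absorption as a metabolic burden, not as protection against low glucose. That is true; the protective reading is an inference from the fact of absorption.

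Finally, the top of the gram range requires four 4.25% bags all stepped down together, which no section describes. It is a bound and should carry little weight.

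**Conclusion.** The point holds, at minor severity and with medium confidence. As written, the rule ties hypoglycemia to a fluid response, one option of which could lower glucose supply in a patient with low glucose, against the section's own aim of metabolic stability.

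The per-bag falls derived above depend on the stated reading of Figure 2. How many patients would be affected is unknown. Nothing in the efficacy analysis or the sample size depends on this point.

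**What to change.** Check the source-language text of the water-loss line in Section 5.1.2. Then replace hypoglycemia with the volume sign that was intended, or delete it. The fluid response for true water loss stays as it is.

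Only if low glucose was really intended, move it to a line of its own, as is done for potassium and calcium, and state there that the dialysate glucose concentration is not to be lowered in response to it.

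The cost is one word in a protocol amendment, plus one sentence in the second case. No visits, tests, patients or CRF items are added.

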The daily use of 1 bag of amino acid peritoneal dialysis fluid is during the nighttime sleep period, while the daily use of 2-4 bags of glucose peritoneal dialysis fluid is during the daytime. The total daily infusion volume, each infusion volume, dwell time, and each excretion volume for each subject are adjusted by the researcher based on individual patient conditions and standardized prescriptions. During treatment, subjects should follow the researcher's guidance for daily life and dietary management, and regularly visit the research center for follow-up and examinations. In the third and sixth months of treatment, subjects should repeat the screening period

All evaluation items and any adverse events or serious adverse events are recorded.

The research process is shown in Table 1:

Table 1: Research process table

Evaluate projects	Screening period/baseline	stage of therapy					
		1 month	2 months	3 months	4 months	5 months	6 months
informed consent	√	×	×	×	×	×	×
Inclusion and exclusion criteria	√	×	×	×	×	×	×
Collect demographic data	√	×	×	×	×	×	×
Symptoms (loss of appetite, nausea, vomiting, abdominal distension, Infusion pain, edema, etc.)	√	√	√	√	√	√	√

Previous illness/treatment	✓	✗	✗	✗	✗	✗	✗
Combination therapy with concomitant medication	✓	✓	✓	✓	✓	✓	✓
allergic history	✓	✗	✗	✗	✗	✗	✗
SGA	✓	✓	✓	✓	✓	✓	✓
check-up	✓	✓	✓	✓	✓	✓	✓
vital sign	✓	✓	✓	✓	✓	✓	✓
Ultrafiltration volume	✓	✓	✓	✓	✓	✓	✓
UPD	✓	✓	✓	✓	✓	✓	✓
BMI	✓	✓	✓	✓	✓	✓	✓
CI	✓	✗	✗	✓	✗	✗	✓
skin-fold thickness	✓	✗	✗	✓	✗	✗	✓
Waist circumference and grip strength, upper arm muscle circumference	✓	✗	✗	✓	✗	✗	✓
Hepatitis B related antigen antibody, hepatitis C antibody, HIV antibody	✓	✗	✗	✗	✗	✗	✗
Biochemistry and liver and kidney function (including serum albumin, Prealbumin), glycosylated hemoglobin	✓	✗	✗	✓	✗	✗	✓
White, fasting blood sugar							
Nt-Pro BNP	✓	✗	✗	✓	✗	✗	✓
nPCR	✓	✗	✗	✓	✗	✗	✓

nPNA	✓	✗	✗	✓	✗	✗	✓
Kt/V and Ccr	✓	✗	✗	✓	✗	✗	✓
PET	✓	✗	✗	✓	✗	✗	✓
adverse event	✓	✓	✓	✓	✓	✓	✓

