5.2 Adjuvant therapy/combined medication

During treatment, in addition to the use of amino acid peritoneal dialysis fluid and glucose peritoneal dialysis fluid, the subjects should also

Continue with their original adjuvant therapy, including:

Nutritional support drugs: if the patient has been taking nutritional drugs before entering the study, continue the original nutritional drug treatment,

No additional nutritional support drugs were added after entering the study.

Antihypertensive drugs: adjust the type of antihypertensive drugs according to the patient's blood pressure level and ultrafiltration. The dose is used to keep blood pressure within the target range.

Antianemia drugs: erythropoietin is adjusted according to the patient's hemoglobin level and iron metabolism. The type and dose of EPO and iron supplements were used to improve anemia.

Calcium and vitamin D drugs: according to the patient's blood calcium, blood phosphorus, parathyroid hormone (PTH) and other indicators

Targets, adjust the types and doses of calcium and vitamin D drugs to prevent and treat renal bone disease.

Phosphorus binder: Adjust the type and dose of phosphorus binder according to the patient's blood phosphorus level and diet. Control blood phosphorus levels within the target range.

Anticoagulant drugs: adjust the type and dose of anticoagulant drugs according to the patient's coagulation function to prevent and treat thrombosis.

Other drugs: other necessary drug therapy, such as anti-infective drugs, is given according to the specific condition of the patient anti-heart failure drugs, anti-arrhythmia drugs, uric acid reduction.

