5.3 Treatment compliance

During the treatment period, participants should use the amino acid peritoneal dialysate and glucose peritoneal dialysate correctly according to the instructions and prescriptions of the researcher, and record each infusion volume, retention time, and output. Participants should submit their daily treatment logs to the researcher for verification and storage. Participants should maintain good peritoneal dialysis techniques and hygiene habits to prevent infections and complications. Participants should regularly visit the research center for follow-up visits and examinations, and promptly report any adverse reactions or discomforts to the researcher. Participants should adhere to dietary, hydration, and exercise recommendations provided by the researcher and avoid using other drugs or treatments that may affect the results of this study. If a participant is unable to continue participating in this study for any reason, they should notify the researcher in a timely manner and explain the reasons for withdrawal follow.

6. Adverse events

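### The potassium rule in section 5.1.2 names replenishment as the action for both low and high potassium (minor; English wording only)

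*Combined protocol and SAP*

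**What the plan says.** Section 5.1.2 opens by letting the researchers adjust dose and frequency "to ensure the patient's water and electrolyte balance and metabolic stability", and then lists specific principles. The potassium principle applies when the patient shows signs of "elevated or decreased blood potassium, the investigator can administer drug therapy to replenish potassium, to maintain normal blood potassium levels".

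The calcium principle follows it and has the same two-way trigger: "elevated or decreased blood calcium, the investigator can adjust the patient's calcium and vitamin D". Section 5.2 handles phosphorus in a similar way: "Adjust the type and dose of phosphorus binder according to the patient's blood phosphorus level and diet".

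Potassium is mentioned in two other places, both of them lists of laboratory tests: item (12) of section 4.1 and the biochemistry paragraph of section 4.2.1. Neither attaches an action to the result.

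**The concern.** As written, the sentence gives a reader facing a high potassium value one named response, and that response would raise the value further. This is operative treatment text for dialysis patients at five planned centres. It is also the only potassium-specific instruction in the document. An investigator who looks to 5.1.2 for the specific action would find the wrong one for half of the trigger. What is at stake is patient safety and the clarity of the treatment instructions. The trial's inference is not involved.

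**Working it through.** No arithmetic beyond counting applies, and the plan states no figure to reproduce. The check sets the relevant texts side by side.

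**1. The rule against its own aim.**

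| Potassium state | Action named | Effect relative to the stated aim (normal level) |
|---|---|---|
| Decreased | Replenish potassium | Towards the aim |
| Elevated | Replenish potassium | Away from the aim |

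**2. The rule against the others in 5.1.2.** The section has five conditional rules.

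| Rule | Trigger | How direction is handled |
|---|---|---|
| Water retention | One direction | Own action (increase) |
| Water loss | One direction | Opposite action (reduce) |
| Potassium | Both directions | One-way action (replenish) |
| Calcium | Both directions | Neutral action (adjust) |
| Nutritional decline | One direction | Own action (increase) |

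Two of the five rules join both directions in one trigger. Of those two, only the potassium rule has a one-way action. The phosphorus binder entry in 5.2 also uses a neutral verb.

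**3. Search for a correcting instruction.** Potassium is mentioned in three places: 4.1 item (12), 4.2.1 and 5.1.2. One of the three (5.1.2) names an action, and none names an action specific to a high value. Section 5.2 has seven entries: nutritional support, antihypertensives, anti-anaemia drugs, calcium and vitamin D, phosphorus binder, anticoagulants, and other drugs. None names potassium.

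**4. Search for provisions that allow correct care.** There are several, all general:
- The lead-in to 5.1.2 on electrolyte balance.
- Prescription adjustment: in 4.1 the infusion and dwell settings "are adjusted by the researcher based on individual patient conditions and standardized prescriptions", and in 5.1.1 they "are determined by the researchers based on the patient's condition".
- Diet: "During treatment, subjects should follow the researcher's guidance for daily life and dietary management" in 4.1 and "Participants should adhere to dietary, hydration, and exercise recommendations provided by the researcher" in 5.3.
- The open-ended last entry of 5.2, which allows other drugs the patient needs.
- The duty in 6.2 to treat adverse events appropriately.
- The allowance in 9.3 for adapting the treatment plan to the individual.

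These let an investigator treat high potassium correctly. None of them changes what the potassium sentence says.

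**The case against.** The strongest reply is that this is a translation slip and not a fault in the plan. The English is damaged in many places and at least once appears to reverse a meaning: section 4.1 calls the amino acid fluid especially suitable for patients with albumin below 35 g/L, while the near-identical product description in 5.1.1 says it is not suitable for them. Section 7.3 describes the treatment as intravenous albumin. A dropped word in the potassium sentence, such as one for lowering or a simple conjunction, would remove the problem. The calcium sentence used for comparison is itself broken a few words later, so it is weak evidence of what the authors intended.

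A second reply is clinical. The ions listed for both fluids in 4.1 and 5.1.1 are sodium, calcium, magnesium, chloride and lactate, with no potassium. Changing the dialysis prescription is therefore a plausible way to lower potassium, and replenishment would be the natural drug action to name. Clinicians would not give potassium for a high value, and the rule says only that they *can*.

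Much of this stands. Translation is a likely explanation, though it cannot be shown without the source text, and whether sites work from a Chinese text is also an assumption. The practical risk is low. Even so, the English sentence still names the wrong action for one of its two triggers, and nothing elsewhere corrects it.

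**Conclusion.** The concern holds, at minor severity. In the English text, one of the five rules in 5.1.2 ties a two-way trigger to a one-way action, and for elevated potassium that action contradicts the rule's own aim. Confidence is high for the English wording and does not extend to the source-language protocol, which was not available.

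No number of affected patients or test values is claimed. The rule is triggered by signs and not by a scheduled test, and the documents give no rate of high potassium. No endpoint, sample size or analysis depends on this sentence.

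**What to change.** First compare the sentence with the source-language protocol. Then replace it with wording that separates the two directions, for example:

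> If blood potassium is decreased, the investigator can replenish potassium; if it is elevated, the investigator can use potassium-lowering measures (drug, diet or dialysis prescription). The aim in both cases is a normal level.

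This keeps the investigator's discretion and the stated aim, and adds the missing direction.

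If the source already separates the directions, only the translation needs correcting. If it has the same fault, a one-sentence amendment and a note to sites are enough. No extra patients, visits or data are needed.
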